2. STUDY SYNOPSIS

T'41 -	The December Of State of a Observation Control of Contr				
Title	A Prospective Study of a Single Injection Cross-linked Sodium Hyaluronate combined				
	with Triamcinolone Hexacetonide (CINGAL®) to Provide Symptomatic Relief of Osteoarthritis of Ankle Joint				
Study	To obtain clinical data to support an expanded indication for a single injection of Cingal®				
Objective Study					
Investigational	used for the symptomatic relief of osteoarthritis in the ankle joint.				
Product	CINGAL®: A chemically cross-linked sodium hyaluronate combined with Triamcinolone Hexacetonide supplied as a 4-mL unit dose in a 5-mL glass syringe.				
Mode of	Cingal will be injected into the intraarticular (IA) space of the index ankle using an 18-21-				
Delivery	gauge needle.				
Benvery	Intra-articular injection of the index ankle joint may be conducted under fluoroscopic or				
	ultrasound guidance as required by standard of care treatment.				
Study Design	Prospective, multi-center, open label expanded indication clinical trial.				
Phase	Phase III				
Sample Size	25 subjects will be enrolled and treated.				
Study Duration	The entire study duration from first subject in to last subject out will be approximately one				
,	and half years. The enrollment phase will be approximately 12 months with a follow-up				
	phase of 6 months. Visits will be scheduled at screening, baseline, 1 month, 3 months				
	and 6 months post treatment. First patient in is expected Nov - Dec 2020.				
Inclusion	Screening Inclusion Criteria				
Criteria	1. Age 18 years or older				
	2. Body Mass Index (BMI) ≤ 35 kg/m²				
	3. Diagnosis of symptomatic osteoarthritic joint in the index ankle (Kellgren-Lawrence				
	grade I to III) to be treated with Cingal injection.				
	4. Failed conservative treatment for joint osteoarthritis.				
	5. NRS pain on walking ≥4 and ≤9 in the index ankle.				
	6. Subject must be willing to abstain from other treatments of the index ankle for the				
	duration of the study. 7. Subject is willing to discontinue all analgesics including NSAIDs, except				
	acetaminophen/paracetamol, at least seven days before the treatment injection and				
	through the completion of the study.				
	8. Subject is willing to use only acetaminophen/paracetamol (up to a maximum of 4.0				
	grams per day per the package insert) for the treatment of joint pain for the duration				

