	A secondary analysis will be conducted on the Per Protocol (PP) population. Since the primary endpoint is at 6 months this is all subjects who complete the 6 month assessment and do not have a major deviation in the conduct of the protocol. For all other visits, this is defined as the subjects who complete those visits according to the protocol.				
	All safety analyses will be conducted on all subjects who undergo treatment of Cingal in the ankle joint.				
Sites	Up to 10 clinical sites in EU				
Sponsor	Anika Therapeutics, Inc. [name], United States of America				
	Phone: + 1 [contact] Fax: + 1 [contact]				

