3. INTRODUCTION

Osteoarthritis (OA) is the most prevalent joint disorder worldwide and is associated with significant pain and disability [1]. It is a progressive disease that can affect any joint but most often involves the weight bearing joints such as the knee. The European Project on Osteoarthritis reported on prevalence rates for knee OA in Europe and the United Kingdom (UK). For subjects aged 65-74 years, the rate of knee OA based on clinical judgment was 36.7% in Italy and 18.6 % in the UK. For subjects aged 75 years or older the rate, based on clinical judgment was 50.8% in Italy. In the Netherlands, the self-reported rate of knee OA in subjects 65-74 years was 23.6% and for subjects 75 years or older was 31.4% [2]. Because of the high prevalence of knee OA, this disease ranked as either the top or second leading cause of disability [3]. In particular, this disease accounted for more dependence on others in climbing stairs, housekeeping and walking a mile than any other disease after adjustment for age, sex and comorbidity [3].

Osteoarthritis is defined as a "heterogenous group of conditions that leads to joint symptoms and signs which are associated with defective integrity of articular cartilage in addition to related changes in the underlying bone and at the joint margins" [4]. OA is characterized by a decreased concentration of HA in synovial fluid and a slow degradation of cartilage over years [5, 6]. The decreased concentration of HA in the synovial fluid of an osteoarthritic joint is probably caused by dilution from exudation, a decreased production of hyaluronans, and increased degradation [6]. Accordingly, the average molecular weight is diminished resulting in a loss of the viscoelastic properties of the synovial fluid for which HA is responsible [5].

Corticosteroids have long been used to alleviate pain and inflammation by injecting into the intraarticular space. Commonly used corticosteroids have been triamcinolone acetonide (TA) and triamcinolone hexacetonide (TH) which have been reviewed in the literature and found to be safe and effective for short term relief of the symptoms of osteoarthritis [7]. Standard dosing for intraarticular injections to the knee for triamcinolone hexacetonide (TH) have been reported as a 1 ml injection at a concentration of 20 mg/ml which will be the proposed dose for the active control in this trial [7].

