6.5 Trial Design

This is a prospective, expanded indications multi-center, open-label study to evaluate the safety and performance of injections of Cingal for relief of pain in patients with a diagnosis of an osteoarthritic ankle joint.

The subjects in this study will be patients with a diagnosis of osteoarthritic (OA) joint who the investigator determines are appropriate candidates for treatment with a viscoelastic injection of Cingal.

Up to 25 subjects will be enrolled and treated at up to 10 investigational sites in the EU. Subject participation will last approximately 6 Months, with visits scheduled at Screening, Baseline, 1 month, 3 month and 6 months.

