2.0 Study Design

This is a prospective, expanded indications multi-center, open-label study to evaluate safety and performance of injection of Cingal for relief of pain in patients with a diagnosis of an osteoarthritic hip joint (CINGAL 20-01), shoulder joint (CINGAL 20-02), and ankle joint (CINGAL 20-03).

The subjects in each of these studies will be patients with a diagnosis of osteoarthritic (OA) joint who the investigator determines are appropriate candidates for treatment with an injection of CINGAL.

In each study, up to 25 subjects will be enrolled and treated at up to 10 investigational sites in the EU. Subject participation will last approximately 6 Months, with visits scheduled at Screening, Baseline, 1 month, 3 month and 6 months.

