4.3 DEMOGRAPHIC AND BASELINE CHARACTERISTICS

All demographic and baseline characteristics will be tabulated by treatment group and a test of homogeneity between the treatment groups will be conducted. For continuous variables (e.g. age, height, weight) a one way ANOVA will be used. For categorical variables (e.g. gender, race), a Fisher's exact test or chi-squared test will be used. Medical history findings, physical examinations and concomitant medications will be tabulated by treatment group.

The baseline, Vital Signs, and BMI data will be summarized via descriptive statistics and tested for homogeneity using a one way ANOVA.

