4.4 ADVERSE EVENTS

All AEs will be coded according to MedDRA. Safety assessments will include Treatment-Emergent Adverse Events (TEAEs) which are defined as AEs with an Investigator assessment of definitely, probably, or possibly related to CTM. TEAEs will be summarized with frequencies and percentages by system organ class and preferred term, severity, and relationship to study CTM for each treatment group. In summaries of TEAEs by severity and relationship to CTM for subjects reporting multiple episodes, all reported events will be included, not only the worst reported case. Serious Adverse Events will also be presented by relationship to the CTM.

The number of subjects with at least one AE will be tabulated for each treatment group. Differences between the treatment groups will be tested using Fisher's exact test. Then the number of AEs for each treatment group will also be tabulated.

The number of subjects and the number of AEs will be tabulated by severity, relationship, and local injection site specific events versus non local events.

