4.5 SUBJECT POPULATIONS

All safety analyses will be conducted on all subjects who undergo treatment in any group.

The Safety Population will be defined as all subjects who undergo at least one Study Treatment, and the safety analysis will be performed on this population.

The primary analysis on the primary endpoint will be performed on the Intent to Treat (ITT) population, defined as all patients who were treated in the study. All Primary and Secondary endpoints will be analyzed using the ITT population.

A secondary analysis will be conducted on the Per Protocol (PP) population. Since the primary endpoint is at 6 Months, this is all subjects who complete the 6 Month visit and who do not have a major deviation from the protocol. For all other assessments, this is defined as the subjects who complete those assessments according to the protocol.

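### SAP 4.3 and 4.4 require tests between treatment groups, but Cingal 20-03 has one open-label group; the tests should go, and the planned AE proportions should carry exact confidence intervals

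*SAP*

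**What the plan says.** **Design.** The protocol synopsis describes the study as "Prospective, multi-center, open label expanded indication clinical trial", and SAP 2.0 does the same: "This is a prospective, expanded indications multi-center, open-label study to evaluate safety and performance of injection of Cingal". Neither document describes randomisation, an allocation ratio or a second treatment. The synopsis sets the safety analysis on one treatment: "All safety analyses will be conducted on all subjects who undergo treatment of Cingal in the ankle joint". The primary analysis (protocol 9.1, SAP 4.1.2) is a one-sample t-test of change from the subject's own baseline.

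**Between-group analyses in the SAP.**
- SAP 4.3: "All demographic and baseline characteristics will be tabulated by treatment group and a test of homogeneity between the treatment groups will be conducted". The methods named are one-way ANOVA for continuous variables and Fisher's exact or chi-squared tests for categorical ones. ANOVA is named again for vital signs and BMI.
- SAP 4.4: "Differences between the treatment groups will be tested using Fisher's exact test".
- SAP 4.5: "All safety analyses will be conducted on all subjects who undergo treatment in any group".

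**The protocol on the same items.** Section 9.2.1 tabulates baseline data by treatment group, with no test. Section 9.2.2 summarises AEs by frequency and percentage, with no test. Section 3 gives a triamcinolone hexacetonide dose, "which will be the proposed dose for the active control in this trial", but no such arm appears in the design, procedures or sample size sections.

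**Scope of the SAP.** One SAP covers three protocols: 20-01 (hip), 20-02 (shoulder) and 20-03 (ankle). It does not define what a treatment group is.

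**The concern.** The tests in SAP 4.3 and 4.4 are stated as commitments, and in a one-group study there is nothing for them to compare. Whoever programmes the SAP has to drop a pre-specified analysis without authority, report a degenerate result, or look for groups elsewhere. The only candidates in the document are the three protocols. A p-value across hip, shoulder and ankle would mix any effect of the joint with differences between non-randomised populations. If non-significant, it could be taken as reassurance about safety.

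Safety is one of the two stated aims (protocol 3, SAP 3.0). The Fisher test is the only inferential step planned for AEs. Once it is recognised as unusable, no planned statement of uncertainty accompanies the AE percentages, in a study of about 25 subjects where that uncertainty is large.

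**Working it through.** **1. The plan's own sample size is for one group.** Inputs from protocol 9.1: mean change 2, SD 2 to 2.5, power 80%, alpha 5%, stated N = 15. For a one-sample t-test the noncentrality is (2/SD)·√n.
- SD 2.5, two-sided 5%: the smallest n with at least 80% power is 15 (power 82.1%), so the stated figure reproduces.
- Other combinations give fewer: SD 2.5 one-sided 12; SD 2 two-sided 10; SD 2 one-sided 8.

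The calculation contains no second group and no between-group difference, which agrees with the design text.

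**2. The planned tests with k = 1 group of 25.**
- One-way ANOVA: between-group degrees of freedom = k − 1 = 0, and the between-group sum of squares is 0. The F ratio is 0/0 over the within-group mean square, so it is undefined. A software check refused the call for want of a second sample.
- Fisher's exact test: with one row, the margins fix the table completely. The observed table has conditional probability 1, so p = 1 for any AE count. The check with 5 of 25 returned p = 1.

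**3. The cross-protocol reading, if someone adopted it.** Assume 25 subjects per protocol and the AE rates below (the rates are assumptions; the documents give none). Power of a pairwise two-sided 5% Fisher test:

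| Assumed AE rates | Power |
|---|---|
| 20% vs 40% | 23% |
| 10% vs 40% | 59% |

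So even a doubling of the AE rate from 20% to 40% would usually be non-significant, and a significant result would concern joints, not Cingal against an alternative.

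**4. What one group can support.** The exact (Clopper-Pearson) 95% interval for x of n takes its lower limit from the 2.5% quantile of Beta(x, n − x + 1) and its upper limit from the 97.5% quantile of Beta(x + 1, n − x). With n = 25 and assumed counts:

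| Subjects with event | Lower | Upper |
|---|---|---|
| 0/25 | 0% | 1 − 0.025^(1/25) = 13.7% |
| 5/25 | 6.8% | 40.7% |
| 10/25 | 21.1% | 61.3% |

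SAP 4.2 sets a 5% level for tests and intervals in general, and SAP 4.1.3.4 specifies exact 95% intervals for responder rates. No section specifies an interval for any AE proportion.

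**The case against.** The strongest reply is that little depends on these tests. The safety endpoint (protocol 6.4, SAP 3.0) is descriptive: incidence, severity and relationship. There is no safety hypothesis, threshold or decision rule. SAP 4.4 already plans TEAE frequencies and percentages by system organ class and preferred term, the number of subjects with at least one AE, SAEs by relationship, and subject and event counts by severity, relationship and local versus non-local site. A one-group ANOVA or Fisher test would show itself to be wrong at programming. Harm would need someone to pool three protocols and then misread the result. A reader can also work out an interval from a reported count and denominator.

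Most of that stands, and it limits the point. Three stronger readings are tempting, and the documents do not support them:
- *That the safety evaluation fails or AE incidence is unplanned.* The descriptive tables answer the safety endpoint and do not depend on the Fisher test.
- *That the SAP intends to compare hip, shoulder and ankle.* It never says so, and several efficacy analyses are specified for each protocol. This reading is only what remains if two or more groups are required.
- *That an active-control arm exists.* The phrase in protocol section 3 is background text with no counterpart elsewhere. Leftover wording is the likelier explanation, as with the SAP's elbow pain score and 1-week column, neither of which fits this study's schedule or joint.

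What the reply does not remove is that the SAP commits to tests that do not fit the design and that its own protocol does not call for. No passage requires AE intervals, so adding them is an improvement, whereas removing or redefining the tests is a necessary correction.

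**Conclusion.** The point holds as an analysis that is wrong as written, in SAP 4.3 and 4.4. For 20-03 the homogeneity ANOVA is undefined and the categorical and AE tests are degenerate. The SAP also goes beyond protocol 9.2.1 and 9.2.2, which contain no tests. The consequence is moderate: the primary efficacy analysis and the descriptive AE tables are untouched, and what is lost is any valid expression of AE precision. At 25 treated subjects that precision is poor, with an upper limit of 13.7% for an event not seen at all and a range of 6.8% to 40.7% for one seen in 5 subjects.

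This rests on two things. The one-group design is inferred from the open-label description, the single treatment given and the one-sample test, since neither document uses the term single-arm. The AE counts and rates are illustrative and not taken from the documents. The correction should be made before the data are analysed.

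**What to change.** - **SAP 4.3:** delete the homogeneity tests, including the ANOVA on vital signs and BMI, and summarise baseline data descriptively for each protocol.
- **SAP 4.4:** delete the Fisher test. For the AE proportions already planned (subjects with any AE, a related AE, an SAE, a local injection-site AE), report n/N, percentage and exact Clopper-Pearson 95% interval, separately for 20-01, 20-02 and 20-03.
- **Across protocols:** state that no test is made between protocols. If a comparison of joints is wanted, define its groups and method and label it exploratory.
- **Wording:** remove the group language from SAP 4.3 to 4.5 and from protocol 9.2.1. Removing the active-control phrase in protocol section 3 is clerical.
- **Alongside this:** settle the AE counting rule before the related-AE proportion is programmed. SAP 4.4 includes all reported episodes, whereas protocol 9.2.2 counts a subject once at the worst severity and strongest relationship. A binomial interval needs one count per subject.

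The cost is SAP text, two small protocol wording changes, and the PROC FREQ call with the BINOMIAL option already specified in SAP 4.1.3.4. No new data or subjects are needed.

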4.5 SUBJECT POPULATIONS

All safety analyses will be conducted on all subjects who undergo treatment in any group.

The Safety Population will be defined as all subjects who undergo at least one Study Treatment, and the safety analysis will be performed on this population.

The primary analysis on the primary endpoint will be performed on the Intent to Treat (ITT) population, defined as all patients who were treated in the study. All Primary and Secondary endpoints will be analyzed using the ITT population.

A secondary analysis will be conducted on the Per Protocol (PP) population. Since the primary endpoint is at 6 Months, this is all subjects who complete the 6 Month visit and who do not have a major deviation from the protocol. For all other assessments, this is defined as the subjects who complete those assessments according to the protocol.

4.6 ADDITIONAL ANALYSES

All of the analyses are performed on the data with the specified covariates or other factors assumed in the model. If it is determined that certain factors may influence the outcomes of the endpoints, then additional analyses will be performed
